#### How Supplied

Starting dose: One starting dose comprises 240 mg given as two 3 mL injections of 120 mg each.

Powder for injection 120 mg:

One vial of DEGARELIX 120 mg contains 120 mg degarelix. Each vial is to be reconstituted with a prefilled syringe containing 3 mL of Sterile Water for Injection. 3 mL is withdrawn to deliver 120 mg degarelix at a concentration of 40 mg/mL.

Maintenance dose: One maintenance dose comprises 80 mg given as one 4 mL injection.

Powder for injection 80 mg:

One vial of DEGARELIX 80 mg contains 80 mg degarelix. Each vial is to be reconstituted with a prefilled syringe containing 4.2 mL of Sterile Water for Injection. 4 mL is withdrawn to deliver 80 mg degarelix at a concentration of 20 mg/mL.

### **Storage and Stability**

Store at 25°C (77°F); excursions permitted to 15-30°C (59-86°F).

Caution should be exercised in handling and preparing the solution of DEGARELIX. Several guidelines on proper handling and disposal of anticancer drugs have been published. To minimize the risk of dermal exposure, always wear impervious gloves when handling DEGARELIX. If DEGARELIX solution contacts the skin, immediately wash the skin thoroughly with soap and water. If DEGARELIX contacts mucous membranes, the membranes should be flushed immediately and thoroughly with water.

### **Clinical Pharmacology**

Degarelix is a GnRH receptor antagonist. It binds reversibly to the pituitary GnRH receptors, thereby reducing the release of gonadotropins and consequently testosterone.

A single dose of 240 mg DEGARELIX causes a decrease in the plasma concentrations of luteinizing hormone (LH) and follicle stimulating hormone (FSH), and subsequently testosterone.

DEGARELIX is effective in achieving and maintaining testosterone suppression below the castration level of 50 ng/dL.

**Pharmacokinetics:** DEGARELIX forms a depot upon subcutaneous administration, from which degarelix is released to the circulation. Following administration of DEGARELIX 240 mg at a product concentration of 40 mg/mL, the mean Cmax was 26.2 ng/mL (coefficient of variation, CV 83%) and the mean AUC was 1054 ng•day/mL (CV 35%). Typically, Cmax occurred within 2 days after subcutaneous administration. In prostate cancer subjects at a product concentration of 40 mg/mL, the pharmacokinetics of degarelix were linear over a dose range of 120 to 240 mg. The pharmacokinetic behavior of the drug is strongly influenced by its concentration in the injection solution.

The distribution volume of degarelix after intravenous (> 1 L/kg) or subcutaneous administration (> 1000L) indicates that degarelix is distributed throughout total body water. In vitro plasma protein binding of degarelix is estimated to be approximately 90%.

Degarelix is subject to peptide hydrolysis during the passage of the hepato-biliary system and is mainly excreted as peptide fragments in the feces. No quantitatively significant metabolites were detected in plasma samples after subcutaneous administration. In vitro studies have shown that degarelix is not a substrate, inducer or inhibitor of the CYP450 or p-glycoprotein transporter systems.

**Excretion:** Following subcutaneous administration of 240 mg DEGARELIX at a concentration of 40 mg/mL to prostate cancer subjects, degarelix is eliminated in a biphasic fashion, with a median terminal half-life of approximately 53 days. The long half-life after subcutaneous administration is a consequence of a very slow release of degarelix from the DEGARELIX depot formed at the injection site(s). Approximately 20-30% of a given dose of degarelix was renally excreted, suggesting that approximately 70-80% is excreted via the hepato-biliary system in

humans. Following subcutaneous administration of degarelix to prostate cancer subjects, the clearance is approximately 9 L/hr.

There was no effect of age, weight or race on the degarelix pharmacokinetic parameters or testosterone concentration.

Common side effects include:

- hot flashes
- injection site pain, redness, and swelling, especially with the first dose
- weight gain
- increase in some liver enzymes
- tiredness
- hypertension
- back and joint pain
- chills
- urinary tract infection
- decreased sex drive and trouble with erectile function (impotence)

Refer to the package insert or manufacturer website for the most complete and up to date information on contraindications, warnings and precautions, and adverse reactions.

#### **10.4 Goserelin acetate implant (Zoladex®) (NSC-606864)**

##### **Pharmacology**

Mechanism of Action: Following initial administration in males, goserelin causes an initial increase in serum luteinizing hormone (LH) and follicle stimulating hormone (FSH) levels with subsequent increases in serum levels of testosterone. Chronic administration of goserelin leads to sustained suppression of pituitary gonadotropins, and serum levels of testosterone consequently fall into the range normally seen in surgically castrated men approximately 2-4 weeks after initiation of therapy.

In females, a similar down-regulation of the pituitary gland by chronic exposure to goserelin leads to suppression of gonadotropin secretion, a decrease in serum estradiol levels consistent with the postmenopausal state, and would be expected to lead to a reduction in ovarian size and function, reduction in the size of the uterus and mammary gland, as well as a regression of sex hormone responsive tumors, if present. Serum estradiol is suppressed to levels similar to those observed in postmenopausal women within 3 weeks following initial administration; however, after suppression was attained, isolated elevations of estradiol were seen in 10% of the subjects enrolled in clinical trials. Serum LH and FSH are suppressed to follicular phase levels within four weeks after initial administration of drug and are usually maintained at that range with continued use of goserelin.

##### **Pharmacokinetics**

1. Absorption: Goserelin 3.6 mg is released slowly in first 8 days, and then rapid and continuous release for the remainder of the 28-day dosing period. Time to peak concentration for goserelin 3.6 mg is 12-15 days in males and 8-22 days in females. Goserelin 10.8 mg

exhibits an initial rapid release resulting in a peak concentration at 2 hours after dosing. From Day 4 until the end of the 12-week dosing interval, the sustained release of goserelin produces a reasonably stable systemic exposure.

2. Distribution: Apparent volumes of distribution determined after subcutaneous administration of 250 mcg aqueous solution of goserelin were 44.1 and 20.3 liters for males and females, respectively. Goserelin is approximately 27% protein bound.
3. Metabolism: Metabolism of goserelin by hydrolysis of the C-terminal amino acids is the major clearance mechanism. The half-life elimination ( $t_{1/2}$ ) is approximately 4 hours in males and 2 hours in females.
4. Elimination: Clearance of goserelin is very rapid and occurs primarily via urinary excretion (>90%; 20% as unchanged drug).

### **Dosing and Administration**

Goserelin is administered subcutaneously into the anterior abdominal wall below the navel line using aseptic technique.

### **Storage and Stability**

Refer to the current FDA-approved package insert for storage, stability and special handling information.

### **How Supplied**

1. Goserelin acetate implant is available in a 3.6 mg or 10.8 mg disposable syringe device. The unit is sterile and comes in a sealed, light- and moisture-proof, aluminum foil laminate pouch containing a desiccant capsule.
2. Goserelin is commercially available and will not be supplied by the study. Refer to the current FDA-approved package insert for additional information.

### **Common side effects**

- Problems getting an erection (impotence)
- Hot flushes and sweats
- Lowered interest in having sex (low libido)
- Temporary bruising and sore skin where you have the injection
- Breast tenderness and swelling

Refer to the package insert or manufacturer website for the most complete and up to date information on contraindications, warnings and precautions, and adverse reactions.

## **10.5 Leuprolide (Eligard®, Lupron Depot®) (NSC-377526)**

### **Pharmacology**

Mechanism of Action: Leuprolide inhibits gonadotropin secretion by acting as a luteinizing hormone-releasing hormone (LHRH) agonist. Continuous administration results in suppression of ovarian and testicular steroidogenesis due to decreased levels of LH and FSH with subsequent decrease in testosterone (male) and estrogen (female) levels. In males, testosterone levels are reduced to below castrate levels. Leuprolide may also act directly on the testes as well as act by a different mechanism not directly related to reduction in serum testosterone.

### **Pharmacokinetics**

1. Absorption: After the initial increase of leuprolide following each injection, mean serum concentrations remain relatively constant.
2. Distribution: The mean steady-state volume of distribution of leuprolide following intravenous bolus administration to healthy male volunteers was 27 L. In vitro binding to human plasma proteins ranged from 43% to 49%.
3. Metabolism: Upon administration with different leuprolide acetate formulations, the major metabolite of leuprolide acetate is a pentapeptide (M-I) metabolite.
4. Elimination: Less than 5% of the leuprolide dose was recovered as parent and M-I metabolite in the urine following the 3.5 mg depot injection.

### **Dosing and Administration**

Leuprolide is administered intramuscular (Lupron Depot®) or subcutaneous (Eligard®) injection based on commercial depot formulation. Injection sites should be varied periodically.

### **Storage and Stability**

Refer to the current FDA-approved package insert for storage, stability and special handling information.

### **How Supplied**

Leuprolide acetate is available in 3.75 mg, 7.5 mg, 11.25 mg, 22.5 mg, 30mg, or 45 mg depot formulation kit with accompanying diluent. The prefilled dual chamber syringe contains lyophilized microspheres of leuprolide acetate incorporated in a biodegradable lactic acid polymer.

Leuprolide is commercially available and will not be supplied by this study. Refer to the current FDA-approved package insert for additional information.

### **Common side effects include:**

- arm, back, or jaw pain
- bloody or cloudy urine
- blurred vision
- burning while urinating
- chest pain or discomfort
- chest tightness or heaviness
- difficult or labored breathing
- difficult, burning, or painful urination
- difficulty with moving
- dizziness
- frequent urge to urinate
- headache
- increased urge to urinate during the night
- muscle pain or stiffness
- nausea
- nervousness

- pain in the joints
- pale skin
- pounding in the ears
- slow or fast heartbeat
- sweating
- troubled breathing with exertion
- unusual bleeding or bruising
- unusual tiredness or weakness
- waking to urinate at night

Refer to the package insert or manufacturer website for the most complete and up to date information on contraindications, warnings and precautions, and adverse reactions

## **11 ADVERSE EVENTS**

### **11.1 Definitions of Adverse Events**

#### **11.1.1 Adverse Event (AE):**

In a clinical study, an AE is any untoward medical occurrence (i.e. any unfavorable and unintended sign [including abnormal laboratory findings], symptom, or disease) in a subject after providing written informed consent for participation in the study. Therefore, an AE may or may not be temporally or causally associated with the use of a medicinal (investigational) product. An adverse event may include the following: an adverse event occurring in the course of the use of a drug in professional practice; an adverse event occurring from drug overdose whether accidental or intentional; an adverse event occurring from drug withdrawal and any failure of expected pharmacological action.

#### **11.1.2 Serious Adverse Event (SAE):**

An SAE is classified as any untoward medical occurrence that, at any dose, meets any of the following criteria:

- Results in death, other than death related to disease progression
- Is life-threatening.
  - The term ‘life-threatening’ in the definition refers to an event in which the subject was at risk of death at the time of the event; it does not refer to an event that hypothetically might have caused death if it were more severe.
- Requires inpatient hospitalization or prolongation of existing hospitalization.
  - A hospitalization or prolongation of hospitalization will not be regarded as an SAE if at least one of the following exceptions is met:
    - The admission results in a hospital stay of less than 24 hours.
    - The admission is pre-planned.  
(i.e. elective or scheduled surgery arranged prior to the start of the study)
    - The admission is not associated with an AE (e.g. social hospitalization for purposes of respite care).
    - However, it should be noted that invasive treatment during any hospitalization may fulfill the criterion of ‘medically important’ and as such may be reportable as an SAE

dependent on clinical judgment. In addition, where local regulatory authorities specifically require a more stringent definition, the local regulation takes precedence.

- Results in persistent or significant disability/incapacity.
  - Disability means a substantial disruption of a person's ability to conduct normal life's functions.
- Is a congenital anomaly / birth defect.
- Is another medically important serious event.
  - An event may be considered an important medical event when, based upon appropriate medical judgment, it may jeopardize the subject and may require medical or surgical intervention to prevent one of the outcomes listed in the definitions above.

### **11.1.3 Adverse Drug Reaction**

Adverse reaction means any adverse event for which there is a reasonable possibility that the drug caused the adverse event. For the purposes of IND safety reporting, 'reasonable possibility' means there is evidence to suggest a causal relationship between the drug and the adverse event. A suspected adverse reaction implies a lesser degree of certainty about causality than adverse reaction, which means any adverse event caused by a drug.

### **11.1.4 Serious Adverse Drug Reaction**

A serious adverse drug reaction is an event that meets any of the criteria for seriousness as previously defined and has a possible causal relationship to the study drugs.

## **11.2 Adverse Event (AE) Reporting**

### **11.2.1 Site Requirements for Recording Adverse Events**

Adverse events (AEs) will be recorded from the time of consent and for 30 days after the last dose of study drugs, regardless of whether or not the event(s) are considered related to the study drugs. The descriptions and grading scales found in the revised NCI Common Terminology Criteria for Adverse Events (CTCAE) v4 will be utilized for AE reporting. A copy of the CTCAE v4 can be downloaded from the CTEP website at <http://ctep.cancer.gov>.

All AEs considered related to study drug will be followed until resolution, return to baseline, or deemed clinically insignificant, even if this occurs post-trial.

### **11.2.2 Site Requirements for Reporting Serious Adverse Events to HCRN**

Site investigators and other site personnel must report any SAEs occurring from the time of informed consent to 30 days after the last dose of study drugs. This includes events both related and unrelated to the study drugs.

The definition of “related” being that there is a reasonable possibility the drug caused the adverse experience.

Unrelated	The Adverse Event is clearly not related to the study drug(s)
Unlikely	The Adverse Event is doubtfully related to the study drug (s)
Possible	The Adverse Event may be related to the study drug (s)
Probable	The Adverse Event is likely related to the study drug (s)
Definite	The Adverse Event is clearly related to the study drug (s)

The completed SAE Submission Form must be sent to HCRN **within 24 hours** of discovery of the event. The form may be sent to HCRN either electronically to [[contact]](mailto:[contact]) or by fax to [contact]. The site investigator is responsible for informing the IRB and/or the Regulatory Authority of the SAE as per local requirements. The original copy of the SAE Submission Form and the fax confirmation sheet must be kept within the Trial Master File at the study site.

Follow-up information should be submitted to HCRN either electronically to [[contact]](mailto:[contact]) or by fax to [contact], using a SAE Submission Form stating that this is a follow-up to the previously reported SAE and providing the follow-up number if appropriate. Each re-occurrence, complication, or progression of the original event should be reported as a follow-up to that event regardless of when it occurs. The follow-up information should describe whether the event has resolved or continues, if and how it was treated, whether the blind was broken or not (if applicable), and whether the subject continued or withdrew from study participation.

### 11.2.3 HCRN Requirements for Reporting Serious Adverse Events to Bayer

HCRN will report all SAEs to Bayer **within 24 hours** of receipt of the SAE Submission Form from the site and to regulatory authorities (FDA) per federal guidelines.

HCRN will report SAEs using a MedWatch form available at <http://www.fda.gov/medwatch/> for SAEs reportable to FDA; all other SAEs will be reported using the HCRN SAE Submission Form. All SAE reports must include the following minimum information:

1. The name and contact information of the reporter
2. The name of the study drug(s)
3. A description of the reported SAE
4. A subject identified by one or more of the following:
  - a. Subject initials
  - b. Subject number
  - c. Knowledge that a subject who experienced the adverse event exists
  - d. Age
  - e. Sex
5. An investigator assessment of study drug causality. For studies with combination therapy, a separate causality assessment should be provided for each study drug.

Additional data, which would aid the review and causality assessment of the case, include, but are not limited to:

- The date of onset
- The severity
- The time from administration of study drug(s) to start of the event
- The duration and outcome of the event
- Any possible etiology for the event
- The final diagnosis or syndrome, if known
- Action(s) taken, if any

All reports shall be sent electronically to:

**Electronic Mailbox:** [[contact]](mailto:[contact])  
**[contact]  
**Address:** Global Pharmacovigilance - USA  
**Mail only:** Bayer HealthCare  
[name]  
[name]

#### **11.2.4 Expedited Reporting of Other Safety Information:**

Sites will report to HCRN **within 24 hours** of discovery of event and HCRN shall report to Bayer **within 24 hours** of receipt of report:

- An adverse event related to study specific procedures which the site investigator reasonably believes impacts subject safety (For Non-SAEs: site investigator decision whether to file to Bayer and other regulatory authorities).
- Any new and important event related to treatment with the study drug(s) which the site investigator reasonably believes impacts subject safety (this is up to the site investigator to determine what is new and important and related to the study drug. Site investigator decision whether to file to Bayer and other regulatory authorities).
- Any pregnancy during which a female patient was exposed to the study drug(s). Any pregnancy in the partner of a male subject, where the male subject was exposed to study drug at the time of conception or conception occurred within two weeks of the last dose of study drug(s).

Any communication, other than communication provided by Bayer, concerning safety related information to regulatory authorities or ethics committees including but not limited to:

Development Safety Update Reports (DSUR) / relevant parts of IND reports for study drugs.  
Any other safety related reports, issues and queries that are either raised by or communicated to regulatory authorities or ethics committees.

#### **11.2.5 Sponsor-Investigator Responsibilities**

HCRN will send a SAE summary to the sponsor-investigator **within 1 business day** of receipt of SAE Submission Form from a site. The sponsor-investigator will promptly review the SAE summary and assess for expectedness and relatedness.

#### **11.2.6 HCRN Reporting to the Food and Drug Administration (FDA)**

HCRN will manage the Investigational New Drug Application (IND) associated with this protocol on behalf of the sponsor-investigator. HCRN will cross-reference this submission to Bayer's parent IND at time of submission.

For protocols conducted under an IND, HCRN will be responsible for all communication with the FDA in accordance with 21CFR312 including but not limited to the 7 and 15 Day Reports, as well as an Annual Progress Report.

#### **11.2.7 IND Safety Reports Unrelated to this Trial**

Bayer will provide to HCRN IND safety reports from external studies that involve the study drug(s) per their guidelines. HCRN will forward safety reports to the sponsor-investigator who will review these reports and determine if revisions are needed to the protocol or consent. HCRN will forward these reports to participating sites **within 1 business day** of receiving the sponsor-investigator's review. Based on the sponsor-investigator's review, applicable changes will be made to the protocol and informed consent document (if required). All IND safety reports will also be made available to sites via OnCore®.

Upon receipt from HCRN, site investigators (or designees) are responsible for submitting these safety reports to their respective IRBs, as per their IRB policies.

## **12. STATISTICAL CONSIDERATIONS**

### **12.1 Study Design**

Newly diagnosed metastatic prostate cancer subjects with  $\geq 2$  bone metastases will be accrued and randomized 1:2 to ADT without or with Radium-223 dichloride respectively. The primary aim of the study is to determine if the addition of Radium-223 dichloride to ADT will improve efficacy in this prostate cancer population. The primary efficacy endpoint is radiographic progression-free survival (rPFS). We expect the control arm with ADT alone to have a 12 month median rPFS. The addition of radium-223 to ADT will target an improvement of 7 months for a median rPFS of 19 months. A total of 140 events are required for at least 90% power to detect Hazard Ratio of 0.632 with a one-sided alpha of 0.1. The study powering is based on assumptions of 19 months median rPFS in the experimental arm and 12 months median rPFS in the control arm. Assuming exponential time to event data, a yearly dropout rate of 10% with

accrual in 24 months and study duration of 48 months, 204 subjects will provide 90% power with a 10% one-sided type I error. Hypothesis testing for the primary endpoint will be conducted at a one-sided 0.10 significance level using a stratified log-rank test. Randomization of 68 subjects to the ADT arm and 136 subjects to the ADT+R arm will be completed with stratification by extent of disease (<6 skeletal metastases without visceral disease versus  $\geq 6$  skeletal metastases or visceral disease) and baseline alkaline phosphatase (normal versus abnormal), abnormal alkaline phosphatase defined as  $> 130$  IU/L. If time anticipated for the number of events required for analysis significantly exceeds 48 months, the sponsor may enroll additional subjects to reach required number of events.

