- CT and MRI scans if clinically indicated can be performed with or without intravenous contrast as per institutional guidelines at screening, C8D1, C13D1 and C17D28 (a window of ± 7 days for all scans is allowed). DEXA scan will be performed at screening and after completion of 1 year of treatment. CT or Brain MRI: Brain imaging studies are not required for eligibility if the subject has no neurologic signs or symptoms suggestive of brain metastasis. Subjects

with neurological symptoms are recommended to undergo a head CT scan (with or without intravenous contrast) or brain MRI (with or without intravenous contrast) to exclude brain metastasis. If brain imaging studies are performed, they must be negative for CNS disease. Skull bone involvement without neurological impact by prostate cancer is allowed. A bone scan will be performed at baseline, C8D1 and after completion of 1 year of treatment.

9. All subjects will receive androgen deprivation therapy with a LHRH agonist (any LHRH agonist such as leuprolide acetate or goserelin acetate is acceptable) or a LHRH antagonist (degarelix) or bilateral orchiectomy per the treating physician. Androgen Deprivation therapy with LHRH agonist or LHRH antagonist will be given continuously.
10. MANDATORY: Serum submission for Bone Turnover Markers: Pre-Dose Cycle 1 Day 1 (late induction group) and thereafter on Day 1 of each cycle during the remaining 6 months of protocol specified therapy and at End of Treatment (both induction groups). CTCs: For following time points only: C1D1 (late induction group only); C2D1 (early induction group only); C4D1; EOT visit. CTCs will be collected for all subjects (n = 204). See Correlative Laboratory Manual (CLM) for collection, labeling and shipping instructions.
11. MANDATORY: Whole blood for banking is to be collected pre dose Cycle 1 Day 1 (late induction group) or pre dose Cycle 2 Day 1 (early induction group) and at EOT. Serum and plasma are to be collected at Pre-Treatment Cycle 1 Day 1 (late induction group) or Cycle 2 Day 1 (early induction group) and at EOT. See CLM for collection, labeling, processing and shipping instructions.

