### 7.8 Maintenance Cycles 14-16 Day 1 ( $\pm 14$ days)

**NOTE:** ADT may continue for up to 2 years from randomization. Maintenance Cycles will = 84 days/12 weeks.

- Laboratory tests:
  - PSA
  - Alkaline phosphatase
- Assessment of adverse events and concomitant medications. This may be done via email, phone call or medical record review

### 7.9 Maintenance Cycle 17 Day 28

- Physical examination. Close monitoring for fractures should be done during all physical exams. If a fracture is suspected radiological exams should be performed per clinical guidelines. Subjects should be encouraged to contact the site investigator for any new onset pain or increase in pain in sites of known bone disease.
- Vital signs including BP measurement, weight, ECOG performance status
- Assessment of adverse events and concomitant medications.
- Laboratory Testing:
  - CMP to include sodium, potassium, chloride, bicarbonate, blood urea nitrogen (BUN), serum creatinine, glucose, calcium, total protein, albumin, AST, ALT, alkaline phosphatase, total bilirubin. Including magnesium, phosphorus
  - CBC (WBC with differential and platelet count, hemoglobin and hematocrit)  
Additional monitoring of CBC w/diff and platelet per site investigator's discretion based on subject clinical status
  - Alkaline phosphatase
  - PSA

- Imaging:
  - CT or MRI abdomen/pelvis
  - Chest x-ray or Chest CT if clinically indicated

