### **8.8 Radiographic Progression-Free Survival**

Time to Radiographic progression or death, whichever occurs first, will be calculated for each subject. Subjects who do not have radiographic progression or death upon follow-up will be censored at their last radiographic assessment.

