### 12.5 Sample Size/Accrual/Study Duration/Replacement Rules

The sample size is 204 eligible and safety evaluable subjects. Accrual of 204 eligible and safety evaluable subjects is expected to take 24 months. Subjects will be followed for 2 years or until the last enrolled subject has progressed, died, has been followed for 24 months, or study is terminated, whichever occurs first. Subjects who are enrolled but do not receive any treatment will be replaced.

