### 12.6 Analysis of Primary Objective

Subjects will be assessed for radiographic progression as described in section 8. Time from first dose of ADT to radiographic progression or death, whichever occurs first, will be calculated for each subject. For subjects who discontinue study treatment due to reasons other than death or investigator assessed progression, every effort will be made to continue tumor assessments on schedule until radiographic progressive disease or subject death. Subjects who do not have radiographic progression or death will be censored at their last measure for radiographic progression. The primary hypothesis test will be conducted at a one-sided 0.1 significance level using a stratified log-rank test. Kaplan-Meier methods will be used to report rPFS graphically by arm including the median rPFS and 12 and 24 month rPFS proportions in the ITT population. The log-rank test without stratification will be used as a sensitivity analysis.

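### The 140 events and 90% power need rPFS observation to a common month 48, which Section 12.5 and the imaging calendar do not clearly provide

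*Combined protocol and SAP*

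**What the plan says.** **Power statement.** Section 12.1 and the synopsis ask for 140 events to detect a hazard ratio of 0.632 (medians 12 and 19 months) at one-sided 0.10. Allocation is 68:136 and yearly dropout is taken as 10%. The power claim itself reads: "accrual in 24 months and study duration of 48 months, 204 subjects will provide 90% power with a 10% one-sided type I error".

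**Follow-up.** Section 12.5: "Subjects will be followed for 2 years or until the last enrolled subject has progressed, died, has been followed for 24 months". The same sentence ends by naming one more limit and by making the earliest of them decisive: "or study is terminated, whichever occurs first". The synopsis row on total study duration gives four years, split into two for accrual and two for follow-up.

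**Imaging.** Footnote 8 of the study calendar places CT/MRI "at screening, C8D1, C13D1 and C17D28 (a window of ± 7 days for all scans is allowed". For bone: "A bone scan will be performed at baseline, C8D1 and after completion of 1 year of treatment". Section 7.8: "ADT may continue for up to 2 years from randomization. Maintenance Cycles will = 84 days/12 weeks".

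**Censoring.** Section 8.8: "Subjects who do not have radiographic progression or death upon follow-up will be censored at their last radiographic assessment". Section 12.6 has the same rule. For subjects who stop study treatment for reasons other than death or progression, it adds that "every effort will be made to continue tumor assessments on schedule until radiographic progressive disease or subject death".

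**Safeguard.** Section 12.3 plans an event count at month 24, blind to arm. Sections 12.1 and 12.3 allow extra enrolment if the required events are expected well after month 48.

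**The concern.** Event-driven power depends on how long event-free subjects remain under observation for the endpoint. A 48-month study with 24 months of accrual gives the earliest subjects up to 48 months each. If each subject is instead followed for two years, or scanned for only 23 months and then censored at the last scan, the later part of that observation is lost.

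At stake are the number of events the trial can expect, the power it can claim, and the timing of the primary analysis. The plan does not say when that analysis is done if 140 events are not reached.

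**Working it through.** **Inputs (Section 12.1 unless noted).** Hazards per month: control ln2/12 = 0.05776; experimental ln2/19 = 0.03648; dropout δ = −ln(0.9)/12 = 0.00878. HR = 12/19, |ln HR| = 0.4595. Assumptions of mine: uniform accrual, progression detected when it occurs, 30.44 days per month.

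**1. Required events.** Schoenfeld, 2:1: D = (1.2816 + 1.2816)² / [(1/3)(2/3)(0.4595)²] = 140.0. This is the plan's figure.

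**2. Common cut-off at month 48.** With k = λ + δ, P(event) = (λ/k)·[1 − (e^(−24k) − e^(−48k))/(24k)].
- Control: 0.780 × 68 = 53.1
- Experimental: 0.640 × 136 = 87.1
- Total 140.1 after rounding. Power = Φ(√(D·2/9)·0.4595 − 1.2816) = 90.0%.

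The design reproduces under this follow-up.

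**3. Two years per subject.** P(event) = (λ/k)·(1 − e^(−24k)).
- Control: 0.692 × 68 = 47.1
- Experimental: 0.534 × 136 = 72.6
- Total 119.7. Power = Φ(√(119.7·2/9)·0.4595 − 1.2816) = Φ(1.088) = 86.2%.

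With dropout hazard 0.10/12 instead, the totals are 140.9 (step 2) and 120.2 (step 3). If the two years run from randomization while rPFS runs from an ADT start up to 28 days earlier, follow-up is at most about 24.9 months: 121.9 events, 86.7%.

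**4. Date of the last scheduled CT/MRI.** Cycles 1–12: 12 × 28 = 336 days. Cycles 13–16: 4 × 84 = 336 days. Day 28 of cycle 17: 27 more days. Total 699 days, or 23.0 months from ADT start. Follow-up to that point gives 46.2 + 70.9 = 117.1 events, 85.6% power.

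**5. Common month-48 close, but no scans after C17D28.** Step 2 minus step 4 leaves 140.1 − 117.1 = 23.0 events to be found through deaths or unscheduled scans. The share found is not given, so the whole range is shown:

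| Share found | Events | Power |
|---|---|---|
| 0% | 117.1 | 85.6% |
| 25% | 122.8 | 86.8% |
| 50% | 128.6 | 88.0% |
| 75% | 134.4 | 89.1% |
| 100% | 140.1 | 90.0% |

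**6. Check by simulation (20,000 trials per scenario).** Each method is compared with its own baseline:

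| Method | Month-48 cut-off | 24 months each | Loss (points) |
|---|---|---|---|
| Formula | 90.0% | 86.2% | 3.8 |
| Stratified log-rank (four equal strata assumed) | 90.4% | 87.1% | 3.3 |
| Unstratified log-rank | 91.0% | 88.0% | 3.0 |

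**7. The month-24 projection.** About 72.3 events are expected by calendar month 24 whichever follow-up rule applies. A projection without a per-subject limit reaches 140 at month 47.9, so the enrolment option would not be prompted. A projection with the two-year limit levels off at 119.7 for 204 subjects and would prompt it. Reaching 140 at 24 months each needs 204 × 140/119.7 = 239 subjects, 35 more.

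**The case against.** **Section 12.5 may intend a common close.** If every subject stops at his own two years, the clause about the last enrolled subject does no work. Taken literally, early progression of that one subject would end follow-up for all, which cannot be meant. A study-level close fits the synopsis duration row and the 48 months in 12.1. This stands: a reader might infer that the plan limits the trial to 120 events, but the documents do not settle it. The two-year limits in calendar footnote 4 (PSA and ALP) and Section 7.10 (subjects off protocol therapy) do not set one for rPFS. A common close still leaves no scan scheduled after C17D28.

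**Section 12.6 asks for continued assessments.** Its sentence covers subjects who stop study treatment. It may also reach event-free subjects at the two-year ADT limit, but it refers to a schedule that has no later dates. Deaths do count as events without a scan, hence the range in step 5.

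**Extra enrolment can restore the events.** This stands in part. The option is discretionary, and Section 12.3 does not say which follow-up limit the projection applies, on which step 7 turns.

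**The loss is small.** It is, for a phase II trial at one-sided 0.10. Ordinary uncertainty does as much: at the month-48 cut-off, 15% yearly dropout gives 132 events and 88.7% power, and a control median of 14 months with the same HR gives 130 and 88.3%. Even the design as stated reaches 140 events in only 54% of simulated trials. But those are uncertainties about the data, whereas this is a mismatch within the plan that can be removed now.

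**Conclusion.** The point holds as an internal inconsistency between the power statement and the follow-up and imaging plan. It is not an arithmetic error: a reader might infer that the sample size was miscalculated, but the sponsor's figures reproduce.

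- If a two-year limit per subject applies and N stays at 204, about 20 of the 140 events are not expected, and power falls by 3 to 4 points.
- If a common month-48 close is meant without later scans, the expected count lies between about 117 and 140.

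The results rest on the plan's exponential medians and dropout rate, uniform accrual, and detection of progression as it occurs. With so few scheduled scans the last assumption is generous, so no count here is a floor.

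The gap produces no bias and no type I error inflation. What is lost is some power and a defined time for the primary analysis.

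**What to change.** Reconcile Section 12.1 and the synopsis with Section 12.5 and the study calendar.

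- **Preferred, if follow-up is about 24 months per subject.** Restate about 120 expected events and about 86% power for 204 subjects (by the formula that gives 140 events and 90%), and say when the primary analysis is done if 140 events are not reached. This is wording only, at the price of a slightly lower stated power.
- **Alternative, if 140 events and 90% power are to be kept.** State in 12.5 and the calendar that rPFS follow-up and imaging of event-free subjects run to a common cut-off (140 events or month 48). The cost is later scans for those still event-free and in follow-up after C17D28, about 14.8 + 48.1 = 63 of 204 on the design assumptions.

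In both cases, add to 12.3 that the blinded month-24 projection applies the actual follow-up and imaging limit per subject. The sentence itself costs nothing. With a 24-month limit it could lead to about 35 more subjects if the sponsor uses the enrolment option.
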